1. BACKGROUND AND RATIONALE

In the UK sustained prevention efforts have not reduced the rate of HIV acquisition by men who have sex with men (MSM) [1]. HIV incidence overall in MSM Genitourinary medicine (GUM) clinic attendees remains at about 1.34% annually, and estimates for Black African heterosexuals (0.17% per year) remain higher than for non-MSM populations overall (0.03% per year). The total cost of caring for those living with HIV will rise inexorably as numbers infected increase. New prevention initiatives are needed to reduce the estimated 4,700 incident infections occurring annually, of which 2,800 occur in MSM. Tenofovir containing regimens used as HIV Pre-Exposure Prophylaxis (PrEP) are highly effective at reducing the risk of HIV acquisition [2-4], and PrEP is recommended as an effective component of an active risk reduction intervention by the European AIDS Clinical Society (EACS) [5], the European Centre for Disease Prevention and Control (ECDC) [6], and the World Health Organisation (WHO) [7].

In the UK, the PROUD trial was designed to measure effectiveness when participants were aware they were taking PrEP. It was stopped early as the high HIV incidence in MSM not on PrEP (9% annually) allowed the strength of PrEP effectiveness to be measured sooner than expected [8]. Therefore, while the safety, efficacy and potential effectiveness of oral PrEP are well established, a number of key questions remain and heterosexual patients were not included in the trial. In this context, NHS England led a programme of work to consider how PrEP as an intervention could be planned and commissioned, based on the available data and plausible assumptions about PrEP eligibility, uptake, adherence and duration of use. Subsequently, PHE advised that before PrEP is used on a substantial scale in England, a better option would be to conduct a trial to address current uncertainties in the policy assumptions. A trial would prioritise these questions about the PrEP 'prevention care continuum' and ensure the required answers are obtained.

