3.4 Number of participants

This trial aims to enrol 13,000 participants.

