3.5 Time period of trial

The trial will last 4.5 years in total, including set-up and closedown. The recruitment period will last for 33 months with all participants completing the trial 36 months from first participant, first visit. The duration for each participant will vary depending when they are first enrolled during the 36 month period e.g. patients who enrol at 33 months would only be on the trial for 3 months. Once recruited, participants may stop and may restart PrEP, according to risk and eligibility, throughout the full duration of the trial.

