Based on the cumulative accrual of over 7,000 in the first 8 months of opening, mainly MSM, the Trial Management Group and independent Steering Committee, supported by the NIHR, have advised NHS England and the Association of the Directors of Public Health (ADsPH) that increasing the original sample size of 10,000 to 13,000 would provide useful additional data and address concerns about the representativeness of those who were recruited to the trial over the initial few months. A trial with 13,000 participants should be sufficient to enable the detection of meaningful differences in duration between sub-groups of participants. However, both the mean and variance of the duration of PrEP use is currently unknown. If there is substantial variance in the duration distribution then excessive differences may fail to be detected in small sub-groups.

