probability of being in one of the states, the proportions in each state, the average duration in a given state, and transition between the states. A panel-data hazards model will be used to take into account difficulties with analysis such as between clinic variation, and the potential for more than one PrEP prescription per participant. A Gaussian random effect model will be used to enable between clinic variation to be modelled. The analysis will allow for subjects to drop out and re-enter the analysis dependent on eligibility status and will allow for multiple periods of PrEP use over time.

All analyses will include subject level covariates to assess differences between sub-groups. A time to event analysis will be used to estimate HIV incidence and will incorporate a 'cure fraction' model to take into account that the large majority of participants will not reach a HIV infection end-point. A mixed effects interrupted time-series analysis will be used to estimate the difference in the numbers of new HIV diagnoses between the pre-trial and during-trial periods in participating clinics. A time series analysis using conditional risk set model will be used to estimate STI incidence in those receiving PrEP due to the recurrent nature of STIs.

In addition, particular care will be required in the interpretation of the analyses due to the potential for risk spectrum¹ and health-seeking behaviour² biases. An outline of how these biases may be investigated and accounted for in the analyses is provided in the statistical analysis plan.

1. Risk Spectrum bias refers to the phenomenon that different clinics may have a different mix of patients in terms of risk. There may also be a difference in risk within clinics over time. For example, those participants who are enrolled into the trial early may report different levels of risk compared to those who are enrolled later on.

2. Health Seeking Behaviour bias refers to the phenomenon that participants coming forward to clinical services may be at different levels of risk compared to those who do not.

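### Section 8.3 adopts a cure-fraction model for HIV incidence because few participants will be infected; that reason does not support such a model, and follow-up of at most 36 months cannot estimate its latent parameters

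*Combined protocol and SAP*

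**What the plan says.** Section 8.3 states: "A time to event analysis will be used to estimate HIV incidence and will incorporate a 'cure fraction' model". The only reason given is that the cure fraction is a "model to take into account that the large majority of participants will not reach a HIV infection end-point". Section 8.3 does not say whether the model is of mixture or non-mixture form, what latency distribution it uses, how a survival plateau would be checked, or which quantity will be reported as incidence. It refers to a SAP for detail, and no separate SAP text is in the document supplied.

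Section 3.5 sets the follow-up: "The recruitment period will last for 33 months with all participants completing the trial 36 months from first participant, first visit". Individual follow-up therefore runs from 3 to 36 months; as the section puts it, "patients who enrol at 33 months would only be on the trial for 3 months". Section 3.5 also allows participants to stop and restart PrEP as their risk and eligibility change. Section 1 expects users' risk to come and go. Section 8.3 itself describes three states between which participants pass: eligible and on PrEP, eligible and off PrEP, and ineligible.

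**The concern.** A cure model assumes that some people can never have the event. It needs either outside grounds for such a group or follow-up long enough for the survival curve to flatten. A low event count supplies neither. Participants here may stay uninfected because HIV is uncommon, because PrEP works, or because the trial closes, and ordinary censoring deals with all three. Susceptibility that varies with behaviour and PrEP use is a time-updated exposure, not a fixed trait at entry. Everyone enrolled was also judged to be at high risk (Section 3.3).

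Three uses of the model are exposed:

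- **Latent quantities.** The cure fraction and the hazard among the susceptible could be read as findings.
- **Covariates.** Section 8.3 promises subject-level covariates in all analyses. Their effects could enter the cure part, the hazard part or both, and the data would hardly tell these apart.
- **Extrapolation.** Section 8.4 feeds HIV risk and PrEP effectiveness into the economic models, with a preliminary report at 25 to 30 months. If those models project the fitted curve forward, a false plateau understates long-term risk.

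**Working it through.** The plan gives no event count, power or precision for HIV incidence, so there is no figure to reproduce. The check asks what a cure model would show if nobody were cured.

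**Inputs from the protocol.** N = 13,000 (Section 3.4). Entry over 33 months with a common close at month 36, so follow-up is 0.25 to 3.0 years (Section 3.5). Incidence of 1.34% per year in MSM clinic attendees overall, 3.3% in MSM with a prior negative test, and 9% in MSM not on PrEP in the earlier UK trial (Section 1).

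**Assumptions.** Rates of 0.13% and 0.45% per year stand in for incidence on PrEP, which the protocol does not give. Entry is uniform, the hazard λ is constant, and there is no other dropout.

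**Step 1: event-free share with nobody cured.** With follow-up uniform on 0.25 to 3.0 years,

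share = [exp(−0.25λ) − exp(−3λ)] / (2.75λ).

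At λ = 0.0134: (0.99666 − 0.96060) / 0.03685 = 97.9%. The other rates give 99.8% (0.13%), 99.3% (0.45%), 94.8% (3.3%) and 86.6% (9%). The condition that Section 8.3 cites is met by censoring alone, even at 9% per year.

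**Step 2: fit a mixture cure model to data with no cured participants.** The model is S(t) = π + (1 − π)exp(−θt), where π is the cure fraction and θ the hazard among the susceptible. There were 60 simulated trials per rate. Ranges are 5th to 95th percentiles.

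| True rate per year | Median 95% profile interval for π (truth 0) | Fits with π above 0.5 | θ, % per year | 1-year cohort risk from the cure model, % | Events/person-years, % |
|---|---|---|---|---|---|
| 0.13% | 0 to 0.996 | 48% | 0.10 to 54.6 | 0.095 to 0.180 | 0.085 to 0.167 |
| 0.45% | 0 to 0.975 | 45% | 0.41 to 20.9 | 0.402 to 0.555 | 0.389 to 0.547 |
| 1.34% | 0 to 0.90 | 38% | 1.23 to 15.8 | 1.22 to 1.51 | 1.21 to 1.49 |
| 3.3% | 0 to 0.60 | 22% | 3.16 to 8.96 | 3.11 to 3.46 | 3.15 to 3.46 |

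The two middle result columns are nearly uninformative at the lower rates. The last two agree closely.

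**Step 3: why.** For small θt, the cohort risk (1 − π)(1 − exp(−θt)) is approximately (1 − π)θt, so the data mainly fix the product (1 − π)θ. One simulated trial at 1.34% per year shows this (289 events, 20,871 person-years):

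- π = 0: θ = 1.38% per year, product 1.38%
- π = 0.5: θ = 2.81%, product 0.5 × 2.81 = 1.41%
- π = 0.9: θ = 15.79%, product 0.1 × 15.79 = 1.58%

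All three lie inside the 95% region: the log-likelihood drops are 0.20, 0.10 and 0.58, against a limit of 1.92. From π = 0 to π = 0.9 the 1-year risk moves only from 1.38% to 1.46% and the 3-year risk from 4.07% to 3.77%. The 10-year risk falls from 12.9% to 7.9%. A Weibull latency gives the same picture and keeps π = 0.95 inside the region, with a 10-year risk of 5.0%.

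**Step 4: front-loaded accrual.** Section 8.1 reports "cumulative accrual of over 7,000 in the first 8 months of opening". With 7,000 entering in months 0 to 8 and 6,000 in months 8 to 33, the median upper limit for π was 0.997, 0.99, 0.95 and 0.90 at 0.1%, 0.2%, 0.5% and 1.34% per year (the first three rates assumed). With a data cut at month 27 and an assumed rate of 0.5% per year, the fitted 10-year risk ran from 1.9% to 5.7%, against a true 1 − exp(−0.05) = 4.9%.

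**Step 5: the plain rate.** In the trial of Step 3, 289 / 20,871 = 1.385% per year, exact Poisson 95% limits 1.230% to 1.554%.

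**The case against.** A reader might infer that the planned HIV incidence estimate is itself unidentified, or that it could come out many times too high. The documents do not support that. Under the same cure model, whole-cohort incidence inside the observed window is well determined. In 100 simulated trials per rate with front-loaded accrual, the cohort rate implied by the cure fit was 1.00, 1.97 and 4.95 per 1,000 person-years, identical to events/person-years at that precision. The largest gap in any one trial was 7%, 3% and 0.7% (assumed true rates 0.1%, 0.2% and 0.5% per year). Nothing in Section 8.3 or 8.4 says that the hazard among the susceptible will be reported as incidence, so setting that hazard beside the true rate compares unlike quantities.

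It is also fair to say that Objective 3 does not rest on this model alone. The comparison of new diagnoses before and during the trial uses a separate interrupted time series with no cure term, and Section 1 describes surveillance-based monitoring of HIV incidence in people taking and not taking PrEP. The SAP may define the reported quantity.

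These points limit the harm. They do not rescue the rationale. No SAP detail can turn a low event count into evidence of immunity, and the protocol gives no reason to expect a plateau within 36 months. Where the cure term does no damage, it also adds nothing to the person-time rate.

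**Conclusion.** Wrong as written, in the stated rationale and the choice of model. With nobody cured, 94.8% to 99.8% of participants would be event-free at rates of 0.13% to 3.3% per year, so the reason given carries no information about a cured group. The cure fraction and the susceptible hazard cannot be separated over 3 to 36 months: at 1.34% per year the interval for the cure fraction spans about 0 to 0.90, and at 0.13% it spans almost the whole range. Covariate effects divided between the two parts, and any projection past month 36, inherit that weakness. Within-trial cohort incidence does not.

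The figures rest on a mixture form with exponential latency (Weibull checked in single simulated trials), a constant hazard, administrative censoring only, no covariates, and assumed on-PrEP rates. Other latency forms would move the interval ends, but they would not supply the missing plateau. Harm to the economic analysis is conditional: it arises only if those models extrapolate the fitted curve or use the latent hazard, and the protocol says neither.

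**What to change.** In Section 8.3 and the SAP:

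1. Make the main HIV incidence estimate events per person-year with exact Poisson limits, overall and by time-updated state (eligible on PrEP, eligible off PrEP, ineligible). The plan already defines these states for its duration analysis.
2. For covariates, use Poisson or piecewise-exponential regression with clinic effects.
3. Drop the cure fraction. Otherwise keep it only as a secondary analysis, with a substantive argument for a non-susceptible group, a stated form and latency distribution, and whole-cohort incidence as the reported quantity rather than the latent hazard.
4. State in Section 8.4 that the economic models take the person-time rates, and that any projection beyond follow-up is a labelled assumption with a sensitivity analysis.

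The cost is a change of wording. No additional data or participants are needed.

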There is little doubt that, when taken correctly, PrEP can significantly reduce the risk of acquiring HIV for an individual. Nonetheless, when delivered at scale to a population, many factors may influence the impact of PrEP. Investigation of each reported HIV seroconversion in those who begin PrEP within the trial will help to assess the extent of PrEP adherence and provide an indication of effectiveness. Another concern about PrEP use is the potential increase in condomless sex with a consequent increase in bacterial STIs, and there is evidence from other countries that this is happening. Participants in PROUD were already at extremely high risk of HIV and other STIs, so extrapolating from these data may be falsely re-assuring. Those accessing PrEP in a large-scale trial may have a lower STI risk prior to taking PrEP and greater

scope for risk compensation when taking PrEP (compared to PROUD participants). However, given HIV and STI incidence has been monitored using GUMCAD in MSM clinic attendee sub-groups for over five years, the population impact of a large-scale PrEP trial on HIV and bacterial STI incidence will be measured both for those taking and not-taking PrEP and stratified by risk markers.

Therefore, this trial aims to address the outstanding questions agreed between Public Health England, NHS England and professional and community stakeholders. For sufficiently robust answers concerning the components of the PrEP continuum of prevention care (% eligible, uptake, duration, etc.) across the heterogeneity of clinics, clinic attendees and eligibility criteria, a trial size of at least 10,000 person years PrEP is required. To mitigate against future geographical inequity in PrEP provision as many clinics as possible should be recruited to the trial. Trial design, methods and data flows should support regular (i.e. quarterly) 'one-to-one' clinical risk assessments to ensure PrEP is delivered 'as part of an active risk reduction intervention including health education and safer sex promotion' [9].

Essential to any future PrEP programme will be the ability to monitor and audit compliance with eligibility criteria and repeated clinical risk assessments. The central role of the GUMCAD information system to the monitoring and evaluation of PrEP has been endorsed by all stakeholders.

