2. TRIAL OBJECTIVES

1. To measure PrEP-eligibility, PrEP-uptake, duration of PrEP-eligibility and duration of PrEP-use (PrEP prevention care continuum) among Genitourinary Medicine (GUM) clinic attendees,
2. To determine whether or not incident HIV infections in trial participants are due to non-adherence or biological failure,
3. To measure change over time in HIV diagnoses and incidence rate in those at high HIV risk,
4. To measure change over time in bacterial STI diagnoses and incidence rate in those at high HIV risk,
5. To measure the PrEP 'prevention care continuum' by clinic throughput and in different regions.

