5 ASSESSMENTS AND FOLLOW-UP PROCEDURES

5.1 Patient Identification

Potentially eligible individuals will be identified by local investigators during routine enquiry about HIV risk at sexual health clinic visits. Potentially eligible individuals may also be identified through outreach activities, by community organisations and through social media. Individuals are also likely to self-identify their need for PrEP as mainstream media has, and will continue to report the plan to implement PrEP through a large scale trial. The participant information sheet will be publicly available through the trial website and individuals will be able to read this prior to visiting clinic, or whilst waiting to be seen. The website will also provide details of participating clinics.

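### The before/during HIV comparison uses diagnosis counts in participating clinics with no stated denominator or comparison series, and no analysis of change in incidence among all high-risk attendees is specified

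*Combined protocol and SAP*

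**What the plan says.** Objective 3 (section 2) is "To measure change over time in HIV diagnoses and incidence rate in those at high HIV risk". It therefore names two measures, diagnoses and incidence rate, in one population, those at high risk.

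Section 8.3 provides two HIV analyses.

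- **Incidence.** "A time to event analysis will be used to estimate HIV incidence", with a cure fraction because "the large majority of participants will not reach a HIV infection end-point". The wording concerns trial participants.
- **Before/during comparison.** A mixed effects interrupted time series "will be used to estimate the difference in the numbers of new HIV diagnoses between the pre-trial and during-trial periods in participating clinics". No offset, testing adjustment or comparison series is named, and the text does not say whether the counts are limited to high-risk attendees. The synopsis names historical controls as the comparator.

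Section 8.3 also says that analyses include subject-level covariates to examine sub-group differences. It names risk-spectrum and health-seeking biases and refers to the SAP for how they may be handled.

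The background (section 1) says that "HIV and STI incidence has been monitored using GUMCAD in MSM clinic attendee sub-groups for over five years". It states an intention to measure population impact on incidence in people taking and not taking PrEP, by risk marker.

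**The concern.** A count of diagnoses depends on how many people attend, how often they are tested and how many are infected. The trial is meant to change the last of these, but it also changes the other two:

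- Section 3.1 requires eligibility screening at each new episode of care.
- Section 5.4.1 calls for HIV testing around PrEP start, and section 5.4.3 advises testing every 3 months.
- Section 5.1 describes outreach and social media recruitment and adds that "Individuals are also likely to self-identify their need for PrEP as mainstream media has" covered the plan.
- Section 8.1 reports over 7,000 enrolments in the first 8 months, so much of the change comes soon after opening, where the model looks for its break.

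Without a denominator, the trial-period term mixes PrEP effect with changes in testing and attendance. Without a comparison series, it also absorbs anything else that alters the trend at about the same time. The result matters beyond this outcome: section 8.4 feeds trial findings on PrEP effectiveness into the economic model, with a preliminary report at about 25 to 30 months.

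**Working it through.** The documents give no effect size, power or event number for the HIV comparison, so there is no planned figure to reproduce. Two checks give the scale.

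**1. Behaviour of a count-based interrupted time series (illustration)**

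The models are noise-free Poisson log-link fits to expected quarterly counts. There are 20 pre-trial quarters (five years, from section 1) and 12 during-trial quarters (36 months, section 6). The base is 700 a quarter (2,800 MSM infections a year in section 1, divided by 4). The trends, rises and true ratio below are assumptions. The trend-and-level model is used except where stated.

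| Scenario | Estimated ratio |
|---|---|
| No PrEP effect; steady decline of 5%, 10%, 20% a year | 1.00, 1.00, 1.00 (crude before/during: 0.81, 0.65, 0.40) |
| No PrEP effect; decline of 10%, 20% a year beginning at trial start | 0.93, 0.85 (with a slope-change term, mid-period: 0.87, 0.74) |
| No PrEP effect; the same declines beginning one year earlier | 0.86, 0.72 |
| No PrEP effect; attendees or tests up 10%, 20%, 30% | 1.10, 1.20, 1.30 |
| True ratio 0.70; same rises | 0.77, 0.84, 0.91 |
| Same rises, log-denominator offset | 1.00 with no effect; 0.70 with a true 0.70 |

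The rows on rises are the true ratio multiplied by the rise, for example 0.70 × 1.30 = 0.91. The offset recovers the truth because diagnoses were assumed to rise in proportion to the denominator. It does not remove a trend change unrelated to PrEP; that needs a comparison series.

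**2. Size of the shift from earlier diagnosis**

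Inputs from the documents: 13,000 participants (section 3.4); 3.3% a year, the background figure for MSM with a prior negative test, applied here to everyone; 3-monthly testing (section 5.4.3); 33 months' recruitment and 36 months in total (section 3.5). Assumed: prior testing every 6 or 12 months, mean diagnostic delay of half the interval, and uniform accrual.

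- Infections a year without PrEP: 13,000 × 0.033 = 429.
- From 12-monthly testing: (6 − 1.5)/12 × 429 = 161 diagnoses brought forward.
- From 6-monthly testing: (3 − 1.5)/12 × 429 = 54.
- Mean follow-up: (36 + 3)/2 = 19.5 months, or 13,000 × 19.5/12 = 21,125 person-years.
- Infections expected over the trial without PrEP: 21,125 × 0.033 = 697.
- Shift as a share: 54/697 = 8%; 161/697 = 23%.
- If everyone were followed for 36 months: 13,000 × 3 × 0.033 = 1,287; 54/1,287 = 4%; 161/1,287 = 13%.

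Participants must be considered HIV negative at enrolment, so much of this shift would appear as positive tests at screening. The 13,000 therefore stands in for the number screened. New attendees would add to the shift.

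**The case against.** Several stronger readings are tempting, and the documents do not support them.

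- A reader might infer that HIV incidence is not estimated at all. Section 8.3 plans a time-to-event incidence analysis, and the background intends population-level measurement. What is missing is a specified analysis of change in incidence among all high-risk attendees. Objective 3 also names diagnoses, so the count series serves part of it directly.
- A reader might infer that any secular decline is credited to PrEP. An interrupted time series projects the pre-trial trend, and the steady-decline scenarios return 1.00. Only a trend change near trial start remains a threat.
- A reader might infer that extra testing exaggerates PrEP benefit. On the count scale it usually hides benefit.
- Setting 54 to 161 against one year's 429 infections gives 13% to 38%, but that compares a one-off shift with one year of a longer trial.

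The defence can also say that section 8.3 refers the detail to the SAP, that it does not rule out an offset, and that HIV diagnoses are outcome 2a while the aim concerns need, uptake and duration. These points lower confidence and importance. They do not settle the matter: the two biases deferred to the SAP concern risk mix and who comes forward, not testing frequency or concurrent trends, and covariates for sub-group differences are not a denominator.

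**Conclusion.** The point holds in a limited form. As written, the before/during series measures diagnoses in participating clinics with no stated denominator or comparison series. Its trial-period effect is therefore confounded with changes in testing and attendance that the trial brings, and with any trend change near its start. The first would usually mask a benefit; the second can bias in either direction, so the net error is not known. The one-off testing shift is 8% to 23% of the infections expected without PrEP (4% to 13% with full 36-month follow-up). This rests on the assumed prior testing intervals, uniform accrual and 3.3% a year throughout.

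The part of objective 3 that asks for change in incidence rate among those at high risk has no specified analysis. Confidence is moderate, because the text available for this review contains no SAP section. If the SAP already specifies an offset, a comparison series and that analysis, section 8.3 need only be aligned with it.

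**What to change.** Keep the diagnosis-count series, since objective 3 names diagnoses, and add the following to section 8.3 and the SAP.

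1. A before/during interrupted time series of HIV incidence per person-year in repeat-testing high-risk attendees, with a log person-time offset and each clinic's own opening date. Define high risk by GUMCAD markers available in both periods (MSM, prior negative test, bacterial STI). The PrEP eligibility codes are new (section 8.6) and cannot define the pre-trial group.
2. The diagnosis series repeated with a log-attendees or log-tests offset, as a secondary analysis. Diagnoses per test fall when the same people test more often, so the tests version can overcorrect.
3. A comparison series from GUMCAD: not-yet-open or non-participating clinics where available, and a lower-risk attendee group defined by the same markers.

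The cost is SAP wording and some analyst time. GUMCAD is mandatory and already covers attendances, service provision and HIV infection (section 8.5), so no new collection is needed. There are limits. Repeat-tester person-time leaves out new attendees. It is also cut short when patients change clinic, because GUMCAD numbers are clinic-specific (section 5.9). Comparison clinics may be few, since the background wants as many as possible to join.
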